### 3.5 Continuation of anticoagulation criteria

Participants will be continued on anticoagulation longer than one month after catheter removal if any of the following criteria exist:

1. Development of thrombosis other than the CRT
2. Extension of the catheter-related thrombosis (i.e. additional vein occlusion on imaging obtained for clinical reasons)

If an enrolled subject at MCW requires anticoagulation longer than 1 month after catheter removal, laboratory assessments will not be completed as the testing can be affected by the presence of an anticoagulant. The participant will not be removed from the study and will be followed for PTS outcomes.

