syndrome using the modified Villalta scale (Appendix I) and functional limitation using the DASH questionnaire (Appendix J). At MCW, surveys will be administered by the TRU staff and physical examination will be completed by BCW nurse coordinator, [name]. At OSU, surveys will be administered by research coordinators trained to complete the assessment. Laboratory samples will be obtained for MCW participants only and processed as noted in section 5.6 and section 6.

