### 5.5 Post-thrombotic syndrome assessments

Visit 2 will occur within 2 weeks of discontinuation of anticoagulation. Visit 3 will be at 3 months after catheter removal plus or minus 2 weeks and Visit 4 within 6 months plus or minus 2 weeks after catheter removal. At each visit, medical history and medication will be reviewed (Appendices E-G). The subjective assessment of the modified Villalta (page 1 and 2 of Appendix I) and the DASH questionnaire (Appendix J) will be administered by the Translational Research Unit (TRU) staff or the clinical nurse coordinator after completing the objective assessment. The objective assessment of the modified Villalta score will be completed by trained clinical nurse coordinators blinded to the subjective assessment (page 3 and 4 of Appendix I). The subjective assessment of the modified Villalta (page 1 and 2 of Appendix I) and the DASH questionnaire (Appendix J), will be administered by the research coordinator at OSU.

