### 5.6 Blood measurements

Blood will be collected by venipuncture using a 20G needle or larger from patients at the BCW site at Visit 2, 3 and 4. A 21G needle may be used for collection of blood via venipuncture if blood cannot be obtained with a 20G needle or larger. The first 2 ml of blood will be discarded due to tissue factor activation with the venipuncture. Three BD Vacutainer citrated tubes (0.105M sodium citrate) with 4.5 ml blood will be collected. Thrombin generation, D-dimer, plasma total TFPI and TFPI $\alpha$ , and platelet TFPI $\alpha$ , will be assayed using platelet-poor plasma (PPP). Thrombin generation will also be assayed using platelet rich plasma (PRP). Laboratory procedures as noted in section 6.

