**Table 2. Study Schedule of Procedures**

Procedure	Screening	Visit 1 (Consent)	Visit 2	Visit 3	Visit 4
Review Eligibility criteria	X	X			
Consent for research participation		X			
Documentation-medical history, medications, &		X	X	X	X

clinical data					
Physical Examination			X	X	X
PTS Assessment: modified Villalta, DASH			X	X	X
Blood draw- D-dimer, thrombin generation, TFPI, plasma free DNA (MCW Only)			X	X	X

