## 7. Subject Remuneration

For their time and efforts in study activities, research subjects will receive \$25 for each of the following patient visits:

- Study visit 2, 1 month after catheter removal
- Study visit 3, 3 months after catheter removal
- Study visit 4, 6 month after catheter removal

A total of \$75 will be paid to subjects completing all study visits to cover travel to the research site, parking, and time of the visits. The subject will be paid \$25 for each completed study visit whether they withdraw, the investigator withdraws them or they complete all study activities. Payment will occur when they are no longer an active participant in the study. Remuneration for study visits will only take place at the BCW site.

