## **11. Statistical Considerations**

### **11.1 Description of Endpoints:**

#### **1. 11.1.1 Feasibility Endpoints:**

- a. Recruitment of 56 patients in 1 year and 80% completion of PTS assessments by enrolled patients.
- b. Feasibility of obtaining plasma samples for biomarker analysis as determined by obtaining 80% of samples from enrolled patients.

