### **11.2 Statistical Analysis**

The incidence of PTS, thrombotic recurrence, major bleeding and clinically relevant non-major bleeding will be reported as proportions. These outcomes will be compared at 3 and 6 months using Chi-square or Fisher's exact tests. A Cox-proportional hazards model will be utilized to calculate the risk of PTS and thrombosis recurrence. Chi-square or Fisher's exact tests will be used to determine if clot presentation or location predicts PTS or thrombotic recurrence. Agreement between the DASH and QuickDASH scales will be assessed using the intraclass correlation coefficient. To compare the discriminating ability of the DASH and QuickDASH on the level of PTS, receiver operating curves will be developed using the scale scores at 6 months as the test variable and dichotomized PTS assessment as the classifying variable. Levels of D-dimer, thrombin generation, and TFPI will be reported as means. Logistic regression will evaluate if D-dimer, thrombin generation or TFPI levels at 1 month or % change from baseline predict thrombotic recurrence. Where necessary, for parametric assumption, we will employ appropriate transformations with justifications. For example, the log of some of the biomarkers data may be used if the data range is >1000. Statistical

significance will be determined with  $p < 0.05$ . SAS version 9.13 and JMP 10 Statistical software will be employed for data analysis.

An interim analysis will be completed after 20 patients complete 6 months of follow-up. The interim analysis will allow assessment of thrombotic recurrence by the DSMC.

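### Section 11.2 uses biomarker change from baseline to predict recurrence, but the first blood sample is the 1-month sample and the outcome is not limited to events after the later draw

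*Combined protocol and SAP*

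**What the plan says.** - **Predictors.** Section 11.2: "Logistic regression will evaluate if D-dimer, thrombin generation or TFPI levels at 1 month or % change from baseline predict thrombotic recurrence". It does not define baseline for the biomarkers, name the visit at which the change ends, or say which recurrences count.
- **Blood draws.** Section 5.6 schedules them "from patients at the BCW site at Visit 2, 3 and 4". Table 2 agrees and marks no draw at Screening or Visit 1. Section 4.1 adds: "Laboratory samples will be obtained for MCW participants only". Ohio State (OSU) patients have clinical assessments only (section 3.1).
- **Timing of Visit 2.** Section 5.5: "Visit 2 will occur within 2 weeks of discontinuation of anticoagulation". Section 7 lists it as "Study visit 2, 1 month after catheter removal". Visits 3 and 4 fall at 3 and 6 months after catheter removal, each plus or minus 2 weeks.
- **Patients without samples.** Under section 3.5, if a Milwaukee (MCW) patient stays on anticoagulation beyond 1 month after removal because of new thrombosis or extension, "laboratory assessments will not be completed as the testing can be affected by the presence of an anticoagulant".
- **Sample target.** Section 11.1.1 judges feasibility of plasma collection "as determined by obtaining 80% of samples from enrolled patients". Section 2.1 gives the same 80% without mentioning enrolled patients.
- **Endpoints.** Section 11.1 lists no endpoint for biomarker prediction of recurrence.

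**The concern.** Set beside the 1-month level, a change from baseline would normally mean a change from a sample taken at or near diagnosis. The schedule contains no such sample: the first draw is the 1-month draw.

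The analyst would therefore have to choose a substitute, and the natural one is change from Visit 2 to a later visit. That raises a problem of order. Suppose a patient has a recurrence between Visits 2 and 3. If the Visit 3 sample is taken, it follows the event, and a rise in D-dimer, for example, may be a consequence of the clot and not a warning of it. If instead the reasoning of section 3.5 is extended to anticoagulation restarted after the recurrence, the sample is not taken and the change is missing. One or the other applies to a given patient, and section 11.2 settles neither. In both cases the event tells us nothing about whether the change predicts recurrence.

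At stake is an association that could look predictive only because the outcome came first, in a model with so few events that one or two such patients could drive it. Unless the definition is fixed beforehand, it could be chosen with the data in view.

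**Working it through.** The plan gives no sample size or event count for the biomarker model, so there is no figure of its own to reproduce. The inputs below do reproduce: 50/(1 − 0.10) = 55.6, rounded up to 56; 36 + 20 = 56 (section 4.2); 20/141 = 14.2%, stated as 14% (section 10.4).

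**Step 1. Which changes can be computed?**

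| Reading of the change | First sample | Second sample | Result |
|---|---|---|---|
| Diagnosis or Visit 1 to 1 month | none scheduled | Visit 2 | cannot be computed |
| Visit 2 to Visit 3 | about 1 month | 3 months | computable; only recurrence after Visit 3 follows both samples |
| Visit 2 to Visit 4 | about 1 month | 6 months | computable; no scheduled follow-up remains after the second sample |

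The level at Visit 2 is available and precedes every recurrence after Visit 2.

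**Step 2. How many events does each usable definition leave?**

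Inputs:
- MCW patients: 36 (section 4.2), less the plan's 10% drop-out, gives N = 36 × 0.9 = 32.4.
- Recurrence risk p: 20/141 = 0.142 or 0.20 (section 10.4). That section gives no time horizon. Assumption: both are 6-month risks counted from catheter removal, with constant hazard.
- Visit 2 at 1.25 months (1 month plus the midpoint of 0–2 weeks), Visit 3 at 3 months, Visit 4 at 6 months.

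Formulas: λ = −ln(1 − p)/6 and F(t) = 1 − exp(−λt). Expected events between times a and b are N × [F(b) − F(a)].

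| Interval | p = 0.142 | p = 0.20 |
|---|---|---|
| Before Visit 2 | 1.0 | 1.5 |
| Visit 2 to Visit 3 | 1.4 | 2.0 |
| After Visit 3 | 2.2 | 3.1 |
| All after Visit 2 | 3.6 | 5.0 |

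Sensitivity:
- Visit 2 anywhere from 1.0 to 1.5 months: 3.4–5.3 events after Visit 2.
- No recurrence before Visit 2: 32.4 × p = 4.6–6.5 after it.
- No drop-out (multiply by 36/32.4 = 1.11): 4.0–5.6 after Visit 2 and 2.5–3.4 after Visit 3.

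On the main assumptions, the events between Visits 2 and 3 are 1.4/3.6 = 39% of those after Visit 2 at the lower risk, and 2.0/5.0 = 40% at the higher. That is the share whose order relative to the Visit 3 sample is wrong for a Visit 2-to-3 change.

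**Step 3. The sample target.**

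Three draws for each of 36 MCW patients gives 108 scheduled samples. 0.8 × 108 = 86.4, so 87 are needed. If draws cancelled under section 3.5 stay in the denominator and everyone else gives all three, 7 patients without samples still pass (29 × 3 = 87; 87/108 = 80.6%) and 8 do not (28 × 3 = 84; 84/108 = 77.8%). Drop-outs who give no blood would use up part of that margin.

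**The case against.** **Undefined, not impossible.** The sentence in section 11.2 does not say that the change ends at 1 month. With Visit 2, the first sample after anticoagulation stops, as baseline, a change to Visit 3 or 4 can be computed, and this gives the later draws a role. That stands. But the plan does not state this reading, and it is the reading that needs a rule on the order of sample and event.

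**Laboratory data from diagnosis.** Section 5.1 obtains laboratory information from the time of diagnosis by record release. That is record data. The study assays are run in batches on plasma from the study draws, and nothing says that thrombin generation or TFPI would be in the record.

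**Section 3.5 already protects the 1-month level.** Its triggers, new thrombosis or extension, match the events counted as recurrence in section 10.4. Most recurrences during anticoagulation therefore fall outside the model already. This stands, and a reader should not take the exclusion for a defect: assay interference is a stated and sound reason. What stays open before Visit 2 is the gap of up to two weeks after stopping.

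**The event counts are assumption.** Also true. The horizon and the constant hazard are imposed, and patients who leave after catheter re-insertion may already have given Visit 2 blood, so 32.4 is not a firm model size. The counts show only how little data the model would have; the problem of definition does not depend on them.

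**A stronger reading of the sample target.** A reader might infer from section 11.1.1 that the 80% target cannot be met, because 20 of the 56 planned patients are at OSU and 36/56 = 64.3%. The documents do not support this. The criterion counts samples, not patients, and OSU has none scheduled. The 64.3% appears only if three draws that nobody planned are imputed to each OSU patient. On MCW samples the target is reachable.

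**Conclusion.** The point holds and is minor. A biomarker change from an earlier baseline to 1 month cannot be computed from the schedule. The reading that can be computed, Visit 2 to a later visit, is not stated, and without a limit on the outcome it admits recurrences that happened before the second sample.

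On the assumptions shown, about 4–5 recurrences would follow Visit 2 and 2–3 would follow Visit 3, so either analysis can only be exploratory. The 1-month level named in the same sentence remains usable for recurrence after Visit 2. The enrolment target and the post-thrombotic syndrome endpoint are unaffected.

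The 80% sample target needs at most a clarification of its denominator; it is not shown to be out of reach.

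**What to change.** In section 11.2:
- Delete change from baseline as a predictor of recurrence, or define it as the change from Visit 2 to Visit 3 and count only first recurrence after Visit 3.
- For the 1-month level, use MCW patients who are recurrence-free at Visit 2 and count only first recurrence after Visit 2.
- Report earlier recurrences separately, and label the model exploratory.

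As an optional clarification in sections 2.1 and 11.1.1, define the 80% target as samples obtained divided by samples scheduled at MCW (87 of 108 if 36 enrol). State in advance whether draws cancelled under section 3.5, or lost after removal for catheter re-insertion (sections 3.4 and 5.4), stay in the denominator.

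The cost is protocol and SAP wording, with no added visits or blood. The downside is that any prediction claim covers later recurrence only and rests on a handful of events, fewest of all for the Visit 2-to-3 change. That favours deleting the change predictor.

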## **4.2 Selection of Subjects**

Subjects will be recruited at MCW and OSU through referral from their treating Hematologist or Oncologist. The patient's treating physician will give potential participants the informational flyer (Appendix A) or use the flyer to verbally describe the study and receive permission for the patient to be screened for eligibility and contacted by the research coordinator. Additionally at Milwaukee and Columbus, an electronic alert will be created that identifies a person with catheter-related thrombosis through the results of their radiology report. The research coordinator will review the report and then contact the treating physician to inform them of the study and receive permission to contact the subject. In 2012, 2350 new patients were seen in the Heme/Onc and BMT clinics at Froedtert Hospital and 1003 had a Port-A-Cath placed. Estimating a catheter-associated thrombotic rate of 15%, this predicts approximately 150 patients annually with CRT due to a Port-A-Cath. Additional patients are anticipated due to CRT from peripherally inserted central catheters (PICC). A survey was conducted among the Heme/Onc and BMT physicians at MCW with a 60% response rate (21/35). The physicians estimated that 63 patients had been seen with CRT in the last 3 months (252 annual). 86% of physicians reported that they would refer patients to a study of CRT treated with 4 weeks of anticoagulation; 14% were uncertain. MCW physicians also noted a variety of treatment practice from 4 weeks to 3 months of anticoagulation after catheter removal. We estimate a 10% drop out rate due to reinsertion of a catheter or inability to remove a catheter. We also estimate that we will need to screen and approach 3 patients for every participant. Therefore, we will plan to screen and approach 250 patients to enroll 56 patients (36 BCW and, OSU 20,) and have 50 complete the study as the overall target.

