## **4.3 Sample Size Estimates**

Sample size estimates were based on the confidence interval method and were based upon the feasibility endpoints. With 50 patients completing the study, we would have 95% confidence that completion of 80% of PTS assessments in the pilot study would correspond to 66-90% completion in another study. Completion of 90% of assessments

would correspond to between 78-96% of assessments. We estimate a 10% drop-out rate so will plan to enroll 56 patients over 1 year.

Evaluation of 50 patients would provide 95% confidence that if the feasibility study found a PTS incidence of 10% that the true proportion in a larger study would not be greater than 20%.

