### 6.2 Thrombin Generation

Thrombin generation will be measured through a calibrated automated thrombogram system (CAT, Thrombinoscope bv, Maastricht, The Netherlands) with and without tissue factor activation using both PRP and PPP. Each well of the 96-well plate will contain 20 ul of reagent (PPP-Reagent or PRP-Reagent), 20 ul of thrombin calibrator, and 80 ul of plasma. Plasma samples will be measured in duplicate.

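### Section 11.2 plans ordinary logistic regression at an unadjusted p<0.05 for 8 biomarker readouts on about 4 to 7 recurrences, giving low power, exaggerated significant odds ratios and uncontrolled false positives

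*Combined protocol and SAP*

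**What the plan says.** Section 11.2 (Statistical Analysis) plans: "Logistic regression will evaluate if D-dimer, thrombin generation or TFPI levels at 1 month or % change from baseline predict thrombotic recurrence". It adds that statistical "significance will be determined with" p<0.05. It does not mention penalised or exact estimation, the test to be used (Wald or likelihood ratio), a primary marker, a multiplicity rule or an exploratory label for the markers.

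The sample behind this regression is set elsewhere:

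- Section 4.1: "Laboratory samples will be obtained for MCW participants only".
- Section 4.2 plans to "enroll 56 patients (36 BCW and, OSU 20,) and have 50 complete the study". The biomarker set is therefore at most 36 patients.
- Section 3.5: for Milwaukee patients who need anticoagulation beyond one month after catheter removal, "laboratory assessments will not be completed as the testing can be affected by the presence of an anticoagulant".
- Section 5.6 and Table 2 place blood draws at Visits 2, 3 and 4, with none at Visit 1.
- Section 6.2 measures thrombin generation "with and without tissue factor activation using both PRP and PPP". Sections 5.6 and 6.4 add D-dimer and three TFPI measures (plasma total, plasma alpha and platelet alpha).
- Section 10.4 gives two recurrence rates: 20/141 (14%) from the institution's own retrospective review, and 20% from other studies.

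**The concern.** Maximum-likelihood logistic regression relies on large-sample theory, and what counts is the number of events, not the number of patients. With single-digit events the estimated log odds ratio is biased away from zero on average. Wald and likelihood-ratio tests then give materially different answers, and only large estimates can reach significance. Testing several readouts at an unadjusted 0.05 adds selection on top.

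Section 1 says the assays will be applied to predict recurrent thrombosis, and section 7.1 names biomarker identification as a possible benefit to others. A false or exaggerated predictor could steer the choice of markers for the larger study that this pilot is meant to inform. With low power, a useful marker could equally be set aside.

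**Working it through.** **1. The plan's own figures.** Section 4.3 sizes the study on feasibility: 50/(1 − 0.10) = 55.6, so 56 enrolled. The Clopper-Pearson 95% interval for 40/50 is 66.3-90.0%, matching the stated 66-90%. These figures reproduce. No event count or power is given for the biomarker regression.

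**2. Expected events = Milwaukee patients × recurrence rate**, at 14.2% (20/141) and 20%.

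| Patients with samples | Events at 14.2% | Events at 20% |
|---|---|---|
| 36 (all) | 5.1 | 7.2 |
| 36 × 0.90 = 32.4 (drop-out, 4.2 and 4.3) | 4.6 | 6.5 |
| 36 × 0.80 = 28.8 (sample target, 11.1.1) | 4.1 | 5.8 |
| 36 × 0.90 × 0.80 = 25.9 (both) | 3.7 | 5.2 |

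This is about 4 to 7. Chance variation matters too: for Binomial(32, 20/141), the probability of 3 or fewer events is about 32%.

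Section 3.5 can lower the count. New thrombosis or extension that prolongs anticoagulation removes the laboratory assessments, and the 14% in section 10.4 counts those same event types. The documents do not say what fraction occurs early. If it were half (an assumption), 1.8 to 3.6 events would remain.

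**3. Number of readouts.** D-dimer 1 + thrombin generation 2 × 2 = 4 + TFPI 3 = 8. Using both level and percent change would make 16.

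**4. Estimation and power.** Simulation with one normally distributed marker per model, assumed true OR 2.0 per SD, 20,000 replicates per row. Excess = ln(back-transformed mean)/ln 2 − 1. The few completely separated datasets are left out of the maximum-likelihood mean.

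| Patients / events | Mean ML estimate as OR | Excess, log scale | Median OR | Firth mean as OR | Power, Wald / LR | Median OR if significant, Wald / LR |
|---|---|---|---|---|---|---|
| 29 / 4 | 2.45 | 29% | 2.12 | 2.02 | 12% / 27% | 6.5 / 5.3 |
| 32 / 5 | 2.35 | 23% | 2.12 | 2.02 | 20% / 31% | 5.0 / 4.2 |
| 32 / 6 | 2.30 | 20% | 2.12 | 2.02 | 24% / 35% | 4.4 / 3.8 |

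Over 3 to 7 events, the mean excess is about 17-30%, the median excess about 5-10%, and Firth is within about 3% of the truth. Power is about 5-30% (Wald) or 22-39% (likelihood ratio). These ranges move by a few points with the number of patients and the handling of separated datasets.

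**5. False positives.** P(at least one of k) = 1 − (1 − α)^k for independent null readouts.

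- Exact 5% tests: k = 8 gives 1 − 0.95^8 = 34%; k = 16 gives 1 − 0.95^16 = 56%.
- Wald: simulated per-test rejection is about 0.8% to 3.2%, so 1 − 0.992^8 = 6% to 1 − 0.968^8 = 23%.
- Likelihood ratio: about 5.5% to 7%, so 1 − 0.945^8 = 36% to 1 − 0.93^8 = 44%.

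Correlation lowers these figures. With 8 normally distributed readouts correlated at 0.5 and 4 to 6 events, the likelihood-ratio figure is about 30-31%.

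**6. Percent change.** Visit 2 is the first draw and is itself the 1-month level, so no earlier sample exists to serve as baseline. If Visit 2 were meant as baseline, the change would come from Visits 3 or 4 and could be measured after the recurrence it is supposed to predict.

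**The case against.** The strongest reply is that this is a pilot. The listed biomarker objective and endpoint concern obtaining 80% of samples (2.1 and 11.1.1). Prediction of recurrence is not among the clinical or secondary endpoints, and no decision rule depends on these p-values. Familywise control in such a setting is partly a matter of preference. That stands. It is why the fix does not demand a multiplicity adjustment or a short list of markers, which could also sideline the novel assays that section 1 sets out to evaluate. It does not justify an estimator and test that work poorly at this event count when a better one costs only wording.

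A reader might also draw stronger conclusions that the documents do not support:

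- That a chance predictor is more likely than not. For 8 readouts the probability stays below one half with either test. It passes 50% with exact 5% tests only if all 16 level and percent-change tests are run and treated as independent. Independence is implausible: the four thrombin-generation conditions share a blood draw, and total TFPI includes the alpha form.
- That only about two events will be available. This needs an early-recurrence fraction that the documents do not give.
- That the typical odds ratio is badly inflated. The median is close to the truth; the distortion lies in the mean and in results picked for significance.
- That a joint model of several markers is planned. Section 11.2 lists the marker families with the word or, and specifies no such model.

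**Conclusion.** The concern holds in this form: ordinary logistic regression at an unadjusted 0.05, on about 4 to 7 expected events from one site and 8 readouts, cannot reliably identify a predictor of recurrence. Low power is at least as serious as false positives. Where Wald tests limit false positives they detect a true OR of 2 at most about 30% of the time; likelihood-ratio tests do somewhat better, at a 36-44% chance of at least one false positive if the readouts are independent. The plan does not say which applies.

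The event count rests on the documents' figures. The bias and power figures rest on an assumed OR of 2 per SD and a normally distributed marker; the false-positive figures for 8 readouts assume independence. The consequence falls on interpretation and on marker choice for the next study, not on the feasibility or post-thrombotic syndrome endpoints.

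**What to change.** In section 11.2, replace the logistic-regression sentence with wording to this effect: each biomarker readout at Visit 2 will be related to later thrombotic recurrence in a separate Firth-penalised (or exact) logistic regression, reported as an odds ratio with a profile-likelihood (or exact) 95% confidence interval; all marker results are exploratory, the number of readouts tested will be stated, and no marker will be called a predictor on p<0.05 alone.

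Also define baseline for percent change, or drop percent change, since no blood is drawn before Visit 2.

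The cost is SAP wording and a check that the software versions named in section 11.2 offer the chosen method. No patients, visits or assays are added. The downside is fewer nominally significant results and wide intervals. The change removes most of the average bias but does not cure low power.

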## 11. Use of anticoagulation >6 months prior to catheter removal

### 3.4 Study Discontinuation Criteria

Subjects may be removed from the study by the Investigator for any of the following reasons:

1. Subject's condition has changed after entering the study so that they no longer meet inclusion criteria, or develop any of the exclusion criteria.
2. Subject experiences an adverse event that warrants withdrawal from the study.
3. Principal investigator determines subject is non-compliant.
4. Subject requires placement of an alternate central venous catheter after discontinuation of enoxaparin or direct anticoagulant therapy.

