#### **10.4 Stopping Rules**

The DSMC can consider stopping the study prior to completion if:

1. The intervention is associated with adverse events that call into question the safety of the intervention
  - a. Interim analysis after 20 patients shows an incidence of thrombotic recurrence >40% (8/20 patients)
    - i. Rationale: A retrospective review of CRT in patients with hematologic malignancy at MCW found development of thrombosis other than CRT or extension of the catheter-related thrombosis in 20/141 (14%) of patients. Recurrent thrombosis has been reported in other studies in 20% of cancer patients. If after half of patients are recruited, the thrombotic incidence has doubled over the reported incidence in the literature, the study will be stopped. This level was chosen because it would be unlikely that if 8 events in the first 20 patients occur that no thrombotic events would occur in the next 20 patients to have an overall 20% (8/40) recurrent thrombosis incidence.

2. Difficulty in study recruitment or retention will significantly impact the ability to evaluate the study endpoints
3. New information becomes available that necessitates stopping the trial

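### The recurrence stopping rule does not say which 20 patients it counts; if they are 6-month completers, fatal recurrences and recurrences followed by withdrawal can drop out of the rate compared with 40%

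*Combined protocol and SAP*

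**What the plan says.** - **Section 11.2 (Statistical Analysis):** "An interim analysis will be completed after 20 patients complete 6 months of follow-up". It adds that this analysis is how the monitoring committee (DSMC) will assess recurrence.
- **Section 10.4 (Stopping Rules), the boundary:** "Interim analysis after 20 patients shows an incidence of thrombotic recurrence >40% (8/20 patients". The lead-in is permissive: "The DSMC can consider stopping the study prior to completion if".
- **Section 10.4, the rationale:** it refers to what follows "if 8 events in the first 20 patients occur", without saying whether those patients are enrolled, treated or completed. It also places the look differently: "If after half of patients are recruited".
- **Section 3.4 (Study Discontinuation Criteria):** the investigator may remove a patient when "Subject experiences an adverse event that warrants withdrawal from the study" (item 2), or when the patient comes to meet an exclusion criterion (item 1). The exclusion criteria in section 3.3 include acute leg deep vein thrombosis and pulmonary embolism.
- **Section 3.5:** a patient whose anticoagulation is prolonged because of a new thrombosis or extension stays in the study and is followed for post-thrombotic syndrome.

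No section says how a recurrence counts in a patient who dies or leaves before 6 months.

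**The concern.** The 8/20 boundary is the plan's only numerical safety limit. The number 20 serves both as the trigger in section 11.2 and as the denominator in section 10.4, so an analyst could readily report recurrences among 20 completers. Completing 6 months depends in part on the outcome being monitored. A patient who dies of a recurrence cannot complete, and a recurrence in the leg or lung can itself be grounds for removal under section 3.4. If such patients are lost more often than patients without recurrence, the rate set against 40% is too low. Two analysts working from the same text could also give the committee different rates.

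**Working it through.** **The plan's own figures.** 8/20 = 40%, which is twice the 20% in "Recurrent thrombosis has been reported in other studies in 20% of cancer patients". 8/40 = 20%, as the rationale states. The local rate, "in 20/141 (14%) of patients", is 20/141 = 14.2%. All three reproduce. However, 8/20 is exactly 40% and so does not satisfy a limit written as more than 40%.

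**If everyone is counted.** The exact binomial chance of at least 8 of 20 is 3.2% at a true recurrence of 20%, 58.4% at 40% and 86.8% at 50%. Reading the limit strictly, as at least 9 of 20, gives 1.0%, 40.4% and 74.8%.

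**If only completers are counted.** Let p be the true 6-month recurrence, f the share of patients with recurrence lost before 6 months, and d the share of the others lost. The expected rate among completers is

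q = p(1 − f) / [p(1 − f) + (1 − p)(1 − d)].

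The documents give neither f nor d. I take d = 10%, which equals the overall dropout in sections 4.2 and 4.3, and vary f. With p = 40%:

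| f (assumed) | q | P(at least 8/20) | P(at least 9/20) |
|---|---|---|---|
| 0% | 0.40/(0.40 + 0.54) = 42.6% | 67.2% | 49.7% |
| 10% | 0.36/(0.36 + 0.54) = 40.0% | 58.4% | 40.4% |
| 25% | 0.30/(0.30 + 0.54) = 35.7% | 42.5% | 25.9% |
| 40% | 0.24/(0.24 + 0.54) = 30.8% | 25.2% | 12.9% |

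With p = 50%, f = 40% and d = 10%, q = 0.30/(0.30 + 0.45) = 40%, and the chance of at least 8/20 falls from 86.8% to 58.4%.

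The direction therefore depends on f against d. Equal loss leaves the rate unchanged. Loss confined to patients without recurrence raises it, towards stopping. Only f greater than d works against stopping.

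**A small example.** Suppose 7 of 20 completers had a recurrence, and 2 further patients with recurrence died or were withdrawn on the way. The completer count is 7/20 = 35%, below the limit. Counting all 22 patients gives 9/22 = 40.9%, above it.

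**The case against.** A reader might infer that the plan excludes these patients, replaces each with the next completer, and is therefore biased against stopping. The documents do not support that, for four reasons.

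- **Section 11.2 fixes when the look takes place.** It does not confine the count to those 20 patients, and section 10.4 speaks of the first 20 patients. Nothing mentions replacement. This stands: the fault is an undefined set, not a stated exclusion.
- **Removal under section 3.4 is discretionary, and section 3.5 keeps some patients with new thrombosis in follow-up.** This stands in part. Section 3.5 does not clearly cover a recurrence after anticoagulation has ended, it sits uneasily with item 1 of section 3.4, and it cannot retain a patient who dies.
- **The direction of bias is not established.** The only dropout the plan quantifies is 10%, for catheter reinsertion or inability to remove the catheter (section 4.2). Neither reason is tied to recurrence. Falling only on patients without recurrence, that loss would push towards stopping. This stands, and it is why the table includes f = 0% and f = 10%.
- **The committee does not depend on this rate alone.** Under section 9.4 all serious adverse events go to it. Under section 10.3 it receives a twice-yearly report with the number of patients entered and a summary of all adverse events. Under section 9.6 it can terminate the study. This limits the harm considerably, but it leaves the rate compared with 40% uncorrected.

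**Conclusion.** The concern holds in a limited form. Sections 10.4 and 11.2 do not define the numerator or denominator of the plan's only numerical safety boundary. The wording of section 11.2 invites a count among completers. Under that count fatal recurrences are missed, and recurrences followed by withdrawal can be. The rule then leans against stopping if, and only if, patients with recurrence are lost more often than others.

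At a true recurrence of 40% and 10% loss of the other patients, the chance of reaching 8/20 runs from 67% with no loss of patients with recurrence to 25% with 40% loss. It is 58% where the two losses are equal. These figures rest on assumed loss rates and on reading the limit as at least 8. They show how sensitive the rule is and do not estimate an actual bias.

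The definition should be settled before the interim look. Because serious events reach the committee by another route, this is a correction worth making and not a fault that leaves patients without oversight.

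**What to change.** In sections 10.4 and 11.2:

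1. Define the interim set as the first 20 patients by order of enrolment, whether or not they complete follow-up. Do not condition on catheter removal, which would drop earlier events.
2. Hold the look once each of the 20 has reached 6 months after catheter removal, has died or has left the study.
3. Count every recurrence among them, including fatal ones and those that led to withdrawal.
4. Report event-free early withdrawals separately, or give a cumulative incidence estimate. Otherwise they are read as full 6-month non-events: if 10% leave at random before any event, a true 40% appears as 0.9 × 40% = 36%, and the chance of at least 8/20 falls from 58% to 44%.

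Three inconsistencies should be reconciled at the same time: items 1 and 2 of section 3.4 with section 3.5, on whether patients with a new thrombosis remain in follow-up; the limit of more than 40% with 8/20; and the timing at half of recruitment in section 10.4 with 6-month completion in section 11.2.

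The cost is a few sentences in the two sections and one clarification between 3.4 and 3.5. No further patients are needed, and recurrences are already collected.
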